12.2 Opioid Medications

A list of patients' concomitant medication records from the CRF data identifying opioid usage will be reviewed by the project team and approved by the sponsor prior to database lock. This listing will be used to flag opioid records in the analysis database and in the by-patient concomitant medication listings.

12.3 Exposure and Compliance

The treatment duration will be calculated and summarized based primarily on CRF data for first and last dose dates (number of days=last dose date – first dose date+1). If these values are missing or patients' diary data indicate dates that exceed this period, the diary dates will be utilized.

Days of exposure will be based on patients' responses to the daily questions regarding medication usage. The number of days on study drug is the total number of days a patient respond that study drug was taken. If the CRF data for the last dose date is a date not included in the diary, it will be added to the count (this should be true for most completing patients since they do not fill out a diary the day of their last visit). The number of patients with total exposure by visit weeks (≤ 2 weeks, 2 to ≤ 4 , 4 to ≤ 8 , 8 to ≤ 12 , 12 to ≤ 14 and ≥ 14 weeks) will be presented. Missing days where the patient did not complete the diary will be treated as though study drug was not taken. Days of exposure will also be calculated for the days on each dose of study drug.

Additionally, the number and percentage of patients that drop back to one tablet per day will be summarized and the week in which they reduced their dose will be tabulated (among those that had a dose reduction).

Compliance will be similarly summarized across all study visits for each treatment arm. Study drug compliance as a percentage will be defined as the exposure days defined above divided by the total number of expected days on treatment multiplied by 100. The expected number of days will be the date of last diary recorded dose-randomization date +1. This compliance reporting

Protocol: TNX-CY-F307 Page 36 of 45

Final v1.0

will take into account whether or not they took any medication, but will not account for the number of tablets they took on a given day.

Compliance will be summarized with descriptive statistics by treatment arm. The number and percentages of patients within certain categories of compliance (e.g. < 60%, 60% to < 80%, 80% to < 100%, greater than 100%) will also be presented.

A listing of drug accountability data based on CRF data will be provided.

Protocol: TNX-CY-F307 Page 37 of 45

Final v1.0

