10.5. Study Drug Accountability and Reconciliation

All patients will be expected to bring their bottles of study drug with them to all study visits (including empty bottles), unless a telephone visit, where patients will be asked to count the number of tablets remaining in their current bottles, document this on a form provided to patient, and return this form and study drug (with bottles) via courier to the site. At each study visit, the site staff will inspect the drug bottles, and perform a count of the tablets remaining in the bottles and document this in the patient's record. For telephone visits, drug accountability by the site staff will occur after the study drug is returned to the site via courier. For home visits (Week 14 or ET only), site staff will collect bottles and conduct accountability upon return to the site. An assessment of drug adherence should be done by the study staff to ensure that the patient understands all dosing instructions and is taking the drug as prescribed. Patients will be asked for an explanation if the count of returned study drug tablets indicates a discrepancy between the expected number of tablets dosed and the number returned in the bottles. If it is found that the patient is not taking the study drug as expected, the patient will be re-counseled with instructions, and this should be noted in the patients' records. A deviation should be recorded on any patient who is less than 70% compliant with dosing between visits and one of the Medical Monitors should be contacted.

Tonix or its designee will perform drug accountability which entails reconciliation between the amount of drug shipped to the study site, study drug assigned and dispensed to the patient (including returned unused assigned study drug), and study supplies that were never dispensed and/or assigned to patients.

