4.4.2 Intermittent Missing Data

Intermittent missing daily data will not be imputed and weekly averages will be calculated using available values, even if only a single value is available for a week. Intermittent missing data (weekly averages and/or in-clinic assessments) occurring prior to discontinuing use of study drug is assumed to be missing at random, and analyses have been chosen to mitigate the impact of these missing data (Section 10.1).

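### SAP 12.3 scores blank diary nights as missed doses, so its exposure-day and compliance tables mix adherence with diary completion

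*SAP*

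**What the plan says.** SAP 12.3 defines three quantities.

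- **Treatment duration** rests on the CRF: "The treatment duration will be calculated and summarized based primarily on CRF data for first and last dose dates". Diary dates are used if the CRF dates are missing or the diary runs beyond them.
- **Days of exposure** rest on the diary: "The number of days on study drug is the total number of days a patient respond that study drug was taken". One addition is allowed: "If the CRF data for the last dose date is a date not included in the diary, it will be added to the count". Blank evenings are then settled against the patient: "Missing days where the patient did not complete the diary will be treated as though study drug was not taken". This count is reported in week bands and split by dose.
- **Compliance** reuses that count: "Study drug compliance as a percentage will be defined as the exposure days defined above divided by the total number of expected days" on treatment. Its denominator is set separately: "The expected number of days will be the date of last diary recorded dose-randomization date +1".

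Protocol 12.2.6 starts the dosing question on the evening of Day 2. Each entry covers the previous night only, and no way of filling in an earlier night is described.

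The protocol also collects a second record. Section 10.1 says returned tablets are counted to assess compliance. Section 10.5 has site staff "perform a count of the tablets remaining in the bottles" and makes dosing compliance below 70% between visits a recorded deviation. SAP 12.3 uses the accountability data only for a listing.

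**The concern.** A blank diary evening shows that the diary was not completed. It does not show that the tablet was not taken. Scoring it as a missed dose lets diary behaviour enter tables that readers will take as statements about dosing.

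The plan handles the same kind of uncertainty differently elsewhere. For the diary scores, SAP 4.4.2 leaves a blank day unimputed and works with what remains: "weekly averages will be calculated using available values, even if only a single value is available for a week". One unanswered evening is therefore unknown for pain and a definite no for dosing. SAP 7 puts patients who do not return all their drug into the Safety population, so uncertain dosing counts as exposed there and as unexposed in 12.3.

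At stake are the exposure bands, the days on each dose and the adherence summary. A patient could be fully compliant by tablet count and poorly compliant in the SAP table, with nothing in the tables to explain the gap.

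**Working it through.** **1. The plan's own figure.** SAP 4.2 gives dosing on Days 1-14 and Days 15-98: 14 + 84 = 98 nights, and 98/7 = 14.0 weeks. This matches the stated 14-week maximum.

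**2. A completer who takes every dose, with Visit 6 on Day 99.** Diary evenings Day 2 to Day 98 report nights 1 to 97. Night 98 comes from the CRF last-dose date. With no blanks, exposure = 97 + 1 = 98 days.

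**3. Scattered blanks.** With *m* blanks, and night 97 answered, exposure = 98 - *m*. The compliance denominator is 97 if the last diary-recorded dose is dated night 97, or 98 if it is dated by the Day 98 entry. The SAP does not say which.

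| Blanks | Exposure days | Weeks | Compliance (/98 to /97) |
|---|---|---|---|
| 0 | 98 | 14.0 | 100.0-101.0% |
| 7 | 91 | 13.0 | 92.9-93.8% |
| 14 | 84 | 12.0 | 85.7-86.6% |
| 21 | 77 | 11.0 | 78.6-79.4% |
| 28 | 70 | 10.0 | 71.4-72.2% |

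At 14 blanks the patient enters the band above 8 and up to 12 weeks. At 20 or 21 blanks compliance falls below 80%. True dosing is 100% in every row.

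**4. The same 28 blanks, all at the end.** The patient answers for nights 1-69, stops the diary and keeps taking the drug to night 98. Exposure = 69 + 1 = 70 days, as in the last row above. The denominator now stops at the last diary-recorded dose, so compliance = 70/69 = 101.4% (70/70 = 100% if dated by entry). Equal diary loss gives 71-72% or 100-101%, depending only on where the blanks fall.

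**5. How often it could matter.** The documents give no completion rate, so the rates below are assumptions. The low end is the entry minimum of 5 days in 7 (Protocol 8.4). Expected exposure for a fully dosed completer is 97*q* + 1. The last column is the binomial chance of at least 14 blanks in 97, taking blanks as independent.

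| Assumed completion *q* | Expected days | Chance of being banded at 12 weeks or less |
|---|---|---|
| 95% | 93.15 | 0.03% |
| 90% | 88.3 | 10% |
| 85% | 83.45 | 61% |
| 80% | 78.6 | 94% |
| 71% (5/7) | 70.3 | above 99.9% |

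**6. After the change.** For the patient with 14 scattered blanks, diary compliance over answered nights is 83/83 = 100%, and exposure is shown as 84 to 98 days. The expected tablet count is 14 x 1 + 84 x 2 = 182, against 40 + 3 x 80 = 280 dispensed, so the return can be compared with a known figure.

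**The case against.** The strongest reply is that this is a disclosed choice to count only confirmed doses. It understates exposure, and it stands beside a CRF treatment duration that diary gaps do not reduce. A reader will see both. Low adherence by tablet count also reaches a by-arm table indirectly, because the 70% threshold generates deviations and SAP 9.2 summarises deviations by type and treatment group. Tablet counts are imperfect too: patients make the first count at telephone visits, bottles carry spares for loss, and SAP 7 expects some drug not to come back. Reminders and site contact after two missed entries (Protocol 12.2.6) should limit long gaps.

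All of this is correct, and it limits the size of the point. It does not remove it. Neither the duration summary nor the deviation table corrects the exposure bands, the days on each dose or the compliance percentage.

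Stronger readings that a reader might infer are not supported:

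- **That the safety rates are distorted.** SAP 8.1 and 11.1 base incidence on patients, each counted once per level. No exposure-adjusted rate is described.
- **That efficacy is affected.** SAP 7 defines no per-protocol set, and the models in SAP 10.1 and 10.2 use no compliance variable.
- **That both measures are always biased downward.** Step 4 of the working shows compliance above 100%.
- **That the tables measure diary habit alone.** Missed doses still lower them.
- **That the arms will differ falsely.** This needs differential diary completion, and the documents give no evidence of it.
- **That 14 blanks always cost two bands.** As the text was extracted, exactly 14 weeks fits both top bands, so the drop may be one.

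**Conclusion.** The point holds for the descriptive exposure and adherence tables. Days of exposure, their week bands, the days on each dose and the compliance percentage report diary-confirmed dosing. For a completer who took every dose, each blank evening removes one exposure day, and 14 scattered blanks give 84 days and 86-87% compliance. Compliance also depends on where the blanks fall, because its numerator can include a CRF dose that lies beyond its denominator.

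The figures assume Visit 6 on Day 99, full dosing and, for scattered blanks, an answer for night 97. How many patients are affected depends on a completion rate that the documents do not give: the effect on the bands is negligible at 95% and large at 85% or below, if blanks are independent. This is worth correcting, but it does not threaten the trial's main conclusions.

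**What to change.** Amend SAP 12.3 as follows.

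1. Treat nights without a diary answer as unknown, and report their number by arm.
2. Compute diary compliance over answered nights only, with numerator and denominator covering the same nights. State whether a dose is dated by the night taken or by the evening of entry.
3. Report days of exposure as two bounds: unanswered nights as not taken (the present count), and unanswered nights as taken, within the CRF first-to-last dose dates. Nights answered no stay out of both.
4. For days on each dose in the upper bound, assign unanswered nights from the CRF-documented dose; Protocol 10.2 already requires reductions to be recorded there.
5. Tabulate tablet-count compliance by arm from the data collected under Protocol 10.1 and 10.5, beside the diary figure, and keep the listing.

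The cost is SAP wording, modest programming and a few more table rows. The upper bound overstates exposure if patients skip the diary and the drug on the same nights. Compliance over answered nights shares this weakness: 14 yes answers and 83 blanks would score 14/14 = 100%. That is why the number of blanks, both bounds and the tablet count belong beside it. The tablet count is itself an imperfect check where bottles are lost or not returned.

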12.2.6. Diary Assessments

The daily diary is an important aspect of this study, and all patients must receive training explaining what is being asked of them, when to complete the diary, and how to use the diary system effectively. Patients will need to receive instructions and a password that uniquely identifies them when they log into the diary system along with instructions about what to do if they have difficulty completing the diary.

The diary should be started the evening of Visit 1 and completed daily until Visit 6 (Week 14). Patients should be instructed to complete the diary in the evening before dosing. Once the patient has properly identified themselves, the diary will prompt answers to the following:

- Rate your average pain during the past 24 hours on a scale from 0-10, where zero is no pain and 10 is worst possible pain.
- Rate your sleep quality last night on a scale from 0-10 where 0 is the best possible sleep and 10 is the worst possible sleep.

After randomization to study drug at Visit 2, the following questions will be added to the daily diary (starting in the evening of the day after randomization, Day 2):

- Did you take your study drug last night? (Yes/No)
- If yes, how many tablets of study drug did you take last night? (1 tablet/2 tablets)

The study staff will be expected to monitor patient adherence in completing the diary throughout the study, and will be instructed to call the patient should any problems or significant non-adherence be observed. During the screening period, there are diary compliance requirements that must be met in order for the patient to qualify for randomization. Patients who have been randomized should be encouraged to continue to complete their diary. Patients will receive a reminder to complete their diary if they miss diary entries. Patients who miss two diary entries will be flagged by the IRT system, and site staff will be alerted to contact patients for re-training and to instruct the patient on the importance of routine completion of their diary.

12.2.7. Assessment of Changes in Sexual Function: Changes in Sexual Functioning Questionnaire Short-Form (CSFQ-14)

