4.2 Method of Treatment Assignment and Randomization

The following randomization criteria must be satisfied at the Baseline visit (Visit 2) in order for the patient to continue in the study and be randomized:

- 1. The patient continues to meet all inclusion and exclusion criteria, including urine and blood test results and is successfully and consistently utilizing the diary system.
- 2. Patient's FM pain satisfies the following criteria, as assessed by diary pain scores (24 hour recall):
 - a. A mean pain intensity score ≥4 and ≤9 on the 11-point (0-10) NRS scale for the 7 days immediately preceding Visit 2, and
 - b. No more than 2 individual days with a score <4 on the 7 days immediately preceding Visit 2, and
 - c. No score of 10 on any of the 7 days immediately preceding Visit 2, and

Protocol: TNX-CY-F307 Page 15 of 45

Final v1.0

d. Pain scores must be recorded on at least 5 out of the 7 days immediately preceding Visit 2.

Before the start of the study, a computer-generated randomization schedule will be prepared. Based on the randomization schedule, eligible patients will be randomly assigned in a 1:1 ratio to receive TNX-102 SL tablets or placebo tablets for 14 weeks.

Treatment A: For Days 1-14, 1 tablet of TNX-102 SL 2.8 mg taken sublingually (under

the tongue) each day at bedtime. For Days 15-98, 2 tablets of TNX-102 SL 2.8 mg (5.6 mg) taken simultaneously and sublingually each day at bedtime.

Treatment B: For Days 1-14, 1 tablet of placebo taken sublingually (under the tongue)

each day at bedtime. For Days 15-98, 2 tablets of placebo taken

simultaneously and sublingually each day at bedtime.

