Each week prior to Week 14 will be based on 7-day intervals; depending on the interval selected for "Week 14", this will result in Week 1 having less than 7 days or some "extra" days prior to Week 1. Extra days will be dropped and not included in the analysis; in the case of less than 7 days, the available days will be averaged, as long as there are non-missing values. The earliest day included in the Week 1 average will be the data entered the day after randomization (covering roughly the 24 hours following their first dose of study drug).

For patients who withdraw from the study early, that do not have a final study visit or complete the study but do not have data in the 7 days preceding their last visit, the last day of diary data (at or prior to Day 106) will serve as the anchor point for dividing the available data into weeks. First, the nearest nominal end day for a weekly period is identified and this week will be the assigned the data from the 7 days immediately preceding the anchor date. For example, if a patient early terminates on study Day 24, the Week 3 (nominally ending on day 21) average will be based on the 7 days prior to Day 24 (Days 17-23). Lost to follow-up patients that continue to fill out the diary into Week 14 and beyond will have non-missing values for the Week 14

Protocol: TNX-CY-F307 Page 21 of 45

Final v1.0

timepoint for diary outcomes. Day 106 will be the last allowable day to be included in the average.

	Nominal Study
Week	Day Intervals
Baseline	Day -7 to -1
Day of	
Randomization	Day 1
Week 1	Day 2 to 7
Week 2	Day 8 to 14
Week 3	Day 15 to 21
Week 4	Day 22 to 28
Week 5	Day 29 to 35
Week 6	Day 36 to 42
Week 7	Day 43 to 49
Week 8	Day 50 to 56
Week 9	Day 57 to 63
Week 10	Day 64 to 70
Week 11	Day 71 to 77
Week 12	Day 78 to 84
Week 13	Day 85 to 91
Week 14	Day 92 to 98

Change from baseline will be defined as the pain score at each week minus the baseline pain score (with baseline and weekly pain scores derived as described above). Thus, negative changes will denote lesser pain and larger negative values will denote greater improvement.

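### SAP 12.3 counts a last dose recorded only on the CRF as exposure but ends expected days at the last diary-recorded dose, so a fully adherent Day 99 completer scores 98/97 = 101.0%

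*SAP*

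**What the plan says.** SAP 12.3 defines compliance as exposure days over expected days, times 100.

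- **Numerator.** Exposure days are the days on which the patient reports having taken study drug, with a possible addition: "If the CRF data for the last dose date is a date not included in the diary, it will be added to the count". The SAP treats the addition as routine: "this should be true for most completing patients since they do not fill out a diary the day of their last visit".
- **Days without an entry.** The exposure paragraph says: "Missing days where the patient did not complete the diary will be treated as though study drug was not taken".
- **Denominator.** "The expected number of days will be the date of last diary recorded dose-randomization date +1".
- **What is counted.** A day counts if any drug was taken, whatever the number of tablets. Results are summarised by arm and in example bands, one of them for values above 100%.

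Under Protocol 12.2.6 the evening diary asks whether drug was taken the night before, and the question is added "starting in the evening of the day after randomization, Day 2". SAP 8.2.1 foresees patients who "complete the study but do not have data in the 7 days preceding their last visit".

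**The concern.** The two parts of a compliance ratio should cover the same nights. Here the dose known only from the CRF enters the numerator, but its date falls after the denominator ends. Because each day can count only once, a valid value cannot exceed 100%, yet the rule gives more than 100% to a patient who did everything right.

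The section also disagrees with itself. It takes treatment duration mainly from CRF dates and uses diary dates where they run later. The same patient would be reported with 98 days of treatment and 97 expected days.

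At stake is whether the compliance table can be read at face value. Fully adherent completers would fall in the above-100% row, and completers who missed one dose would look perfect.

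**Working it through.** **Inputs**

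- Dosing starts on the evening of Day 1 (SAP 4). SAP 4.2 then gives, for the active arm, "For Days 15-98, 2 tablets of TNX-102 SL 2.8 mg (5.6 mg) taken simultaneously and sublingually each day at bedtime", and placebo follows the same days. That is Days 1-98, or 14 × 7 = 98 nights.
- The final visit is targeted for Day 99, when study drug is returned (Protocol 11.5.1).
- An entry on Day d reports the dose of Day d - 1, starting on Day 2 (Protocol 12.2.6).
- For a Day 99 visit the last entry is Day 98 (SAP 8.2.1). SAP 8.2.2 confirms the lag for the sleep item in the same diary: the last night covered is Day 97-98.

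The documents print no compliance percentage, so there is no stated figure to reproduce.

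**Formulas.** Let k be the last entry day and L the CRF last dose day.

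- Exposure days = doses reported for nights 1 to k - 1, plus 1 if L is later than k - 1.
- Expected days as written = last diary-recorded dose day - 1 + 1.
- Expected days with one end date = later of L and last diary-recorded dose day, - 1 + 1.

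**Results**

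| Case | Exposure | As written | One end date |
|---|---|---|---|
| Day 99 visit, all doses, full diary | 97 + 1 = 98 | 98/97 = 101.0% | 98/98 = 100.0% |
| Same, one dose missed on any of Days 1-96 | 96 + 1 = 97 | 97/97 = 100.0% | 97/98 = 99.0% |
| Same, 20 doses missed within Days 1-96 | 77 + 1 = 78 | 78/97 = 80.4% | 78/98 = 79.6% |
| Day 95 visit, all doses | 93 + 1 = 94 | 94/93 = 101.1% | 94/94 = 100.0% |
| Day 106 visit, all doses | 104 + 1 = 105 | 105/104 = 101.0% | 105/105 = 100.0% |
| Early stop, doses Days 1-14, last entry Day 14 | 13 + 1 = 14 | 14/13 = 107.7% | 14/14 = 100.0% |
| Same, but diary also completed on Day 15 | 14 | 14/14 = 100.0% | 14/14 = 100.0% |
| Last entry Day 91, CRF last dose Day 98 | 90 + 1 = 91 | 91/90 = 101.1% | 91/98 = 92.9% |

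The 20-dose row shows that a patient can cross the example 80% band edge. The last three rows depend on what happens to be recorded.

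**Which dating fits the text.** For the fully adherent Day 99 completer:

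- Previous-night dating throughout: Day 98 is not in the diary, the CRF adds it, and the ratio is 98/97 = 101.0%.
- Entry-day dating in the denominator only: 98/98 = 100.0%.
- Entry-day dating throughout: Day 98 already has an entry, nothing is added, and the ratio is 97/98 = 99.0%.

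The SAP says the addition applies to most completers because they make no entry on the visit day. An entry on Day 99 would have reported the Day 98 dose, so the remark makes sense only if answers belong to the previous night. Under entry-day dating throughout, the addition would not be needed.

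**How far the lapse figure can be trusted.** In the Day 91 case, nights 91-97 are unrecorded. If j of those 7 doses were taken, true compliance is (91 + j)/98. At j = 7 it is 100.0%: the written rule is 1.1 points too high and the aligned rule 7.1 points too low. At j = 5 it is 96/98 = 98.0%, with the written rule 3.2 points off and the aligned rule 5.1. At j = 4 it is 95/98 = 96.9%, with the two rules 4.2 and 4.1 points off. The written rule is closer whenever at least 5 of the 7 were taken.

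**The case against.** The strongest reply is that SAP 12.3 never says how a diary dose is dated. SAP 8.2.2 assigns the sleep item, which also looks back one night, to weeks by the date of collection. If the denominator followed that rule, the perfect completer would score 98/98 = 100.0%. It stands that the SAP should state its convention. But the collection-date rule only places sleep answers in weekly averages; it does not date doses. Using it for the denominator alone means two conventions in one ratio, which the SAP does not state.

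A second reply is that the above-100% band shows such values were expected. A band can catch conflicting dates, but it does not justify a rule that puts typical adherent completers there.

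The reply is right about the larger figures. A reader might infer that the rule overrides the SAP's own treatment of days without an entry, and that compliance is overstated by 101.11 - 92.86 = 8.25 points after a Day 91 lapse. The documents do not support that. The sentence on missing entries governs exposure days, and the numerator obeys it: 91 days are counted, not 98. Nothing extends it to expected days, and true intake on the unrecorded nights is unknown. So 92.9% is what one end date would give, not a proven true value. The 107.7% case also disappears if the patient makes one more entry.

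**Conclusion.** The point holds as a small error in a stated derivation. For a Day 99 completer with a full diary the figure is about 1 percentage point too high: 101.0% for 100.0%, or 100.0% for 99.0% with one dose missed on Days 1-96. Gaps after an early stop or a late lapse can be larger, but they are conditional illustrations, and the documents do not say how many patients would have them.

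The result rests on previous-night dating and on a last dose on Day 98. Protocol 11.3 gives the two-tablet period as Days 15-99, against Days 15-98 in the Protocol synopsis and SAP 4.2. Those passages must be reconciled; the counts here use SAP 4.2.

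A reader might infer that the error reaches the efficacy results or the handling of non-adherent patients. It does not. The specified efficacy models and sensitivity analyses do not use this measure, the rule is the same in both arms, and site monitoring uses tablet counts with its own 70% threshold (Protocol 10.5). Only the descriptive compliance table and its bands are affected.

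**What to change.** In SAP 12.3:

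1. Define expected days = (later of CRF last dose date and last diary-recorded dose date) - randomization date + 1. This follows the later-date logic already used there for treatment duration.
2. State that each diary answer is dated to the previous night's dose.
3. Make sure the final bands include exactly 100%. As printed, the example bands run from 80% to below 100% and then above 100%. They are only examples and a symbol may have been lost in text extraction, so this needs checking rather than correcting. An above-100% row can stay as a check for conflicting dates.

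The cost is a wording change and one derivation line, with no new data. The downside is that unrecorded nights before the CRF last dose now lower the figure, so a patient who took the drug but left the diary blank may look less compliant than they were (92.9% in the Day 91 case). A footnote to the table should say so.

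The change does not make the measure complete, because expected days still end at the last dose taken. A patient who stops at Day 60 and keeps answering No to Day 98 scores 60/60 = 100.0% under either rule.
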